### 8.4.2 Rate of MES per hour (before and after treatment, before CEA)

The rate of MicroEmbolic Signals (MES) as assessed at Visit 1 and at Visit 3 will be summarized using descriptive statistics. Data will be analysed from the central reading lab.

Groups will be compared for

- difference of MES at Visit 1 versus post treatment at Visit 3 (delta MES) and
- percent change of MES at Visit 3 compared to Visit 1 (delta MES)

using the ANOVA.

In a subgroup analysis, only patients will be compared who did not receive any change in the concomitant medication with anti-platelet activity (=rescue medication) between the initial assessment at V1 and the follow-up investigation at V3 / V5.

In addition normality of distribution will be checked based on goodness of fit tests. If normality can not be assumed sensitivity analysis will be performed using the Wilcoxon test.

### 8.4.3 Assessment of neurological status (NIH Stroke Scale)

The neurological status was assessed at Visit 2, Visit 5, and Visit 6 by the NIH stroke scale. It comprises 15 items.

1a	Level of Consciousness		0	1	2	3		
1b	LOC Questions		0	1	2			
1c	LOC Commands		0	1	2			
2	Best Gaze		0	1	2			
3	Visual		0	1	2	3		
4	Facial Palsy		0	1	2	3		
5a	Motor Arm	left arm	0	1	2	3	4	9
5b		right arm	0	1	2	3	4	9
6a	Motor Leg	left leg	0	1	2	3	4	9
6b		right arm	0	1	2	3	4	9
7	Limb Ataxia		0	1	2			
8	Sensory		0	1	2			
9	Best Language		0	1	2	3		
10	Dysarthria		0	1	2			
11	Extinction and Inattention		0	1	2			
Total Score			Maximum = 62					

with rating options on the scale 0, 1, 2, 3, 4 and 9 depending on the single item.

Frequencies of scale values will be summarized by visit and by item. Comparison between groups will be performed using the Mantel-Haenszel Chi-square test.

The total score of the NIH Stroke Scale will be compared between groups by visit using ANOVA.

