7.1.2. Visit 2: Treatment

- Physical examination/ vital signs
- Review of concomitant medication
- The trial participant will be given the opportunity to report adverse events (AE) spontaneously, a general prompt will also be given, all adverse events will be followed up until resolution or stabilisation
- Assessment of neurological status (MRS, Barthel Index, NIH Stroke Scale)
- Before administration of study medication, in vitro bleeding time PFA100 / PFA200 and platelet aggregation assay (response to collagen, ADP and TRAP)
- Before administration of study medication, a blood sample for detection of anti-Revacept antibodies will be collected (negative control)
- Pharmacokinetic blood sampling (for approximately 20 % of patients)
 - **t0** prior to IMP administration,
 - **t 0.5h** 30 mins (\pm 5 mins) after start of IMP infusion
 - **t 6h** 6 h (\pm 1 hr) after start of IMP infusion
- **Administration of study medication** will be performed by intravenous infusion for 20 minutes; the time of administration must be recorded.

7.1.3. Visit 3: 24 hrs after treatment (between 2 hrs and 46 hrs after treatment)

- Physical examination/ vital signs
- Review of concomitant medication

- Assessment of AEs
- TCD RECORDING
- ECG examination
- clinical biochemistry, clinical haematology (incl. assessment of bleeding according to RE-LY study group criteria), coagulation and urinalysis
- in vitro bleeding time PFA100 PFA200 and platelet aggregation assay (response to collagen, ADP and TRAP)
- Pharmacokinetic blood sampling (for approximately 20 % of patients)
 - **t24h** 24 hours (\pm 4 hrs) after start of IMP infusion

7.1.4. Visit 4: CEA / intervention (3 days after treatment, -69 hrs / + 5 days)

- Physical examination/ vital signs
- Review of concomitant medication
- Assessment of AEs
- in vitro bleeding time PFA100 /PFA200 and platelet aggregation assay (response to collagen, ADP and TRAP)

THEREAFTER CEA SURGERY OR OTHER INTERVENTIONS CAN BE PERFORMED WITHOUT DELAY

- Pharmacokinetic blood sampling (for approximately 20 % of patients)
 - **T3d** 3 days (\pm 48 hrs) after start of IMP infusion

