9.3.3. Missing Values

Rules on how missing values of efficacy variables will be replaced are to be described in the Statistical Analysis Plan.

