### **6.3 Per Protocol Set**

The PP population includes all subjects who are eligible for ITT evaluation and who, in addition, do not show major protocol deviations.

Exclusion criteria for the study are:

- Extracranial carotid artery stenosis (diagnosed by vascular duplex ultrasound peak flow or angiography) - Lesions with < 50 % stenosis according to European Carotid Surgery Trial (ECST) criteria
- NIHSS score > 18
- Recent intracerebral haemorrhage by X-ray computed tomography (CT) or nuclear magnetic resonance (NMR)
- Cardiac cause of embolisation (atrial fibrillation or other cardiac source e.g. artificial heart valves)
- History of hypersensitivity, contraindication or serious adverse reaction to inhibitors of platelet aggregation, hypersensitivity to related drugs (cross-allergy) or to any of the excipients in the study drug
- History or evidence of thrombocytopenia (<30.000/ $\mu$ l), bleeding diathesis or coagulopathy (pathological international normalised ratio (INR) or activated partial thromboplastin time (aPTT))
- Thrombolysis within the last 48 hours
- Relevant haemorrhagic transformation as determined by CT or anamnesis
- Oral anticoagulation or dual anti-platelet therapy within aspirin or clopidogrel and other P2Y inhibitor at screening (3 days for dipyridamole extended release; 8 hours for tirofiban/Aggrastat)
- Sustained hypertension (systolic BP >179 mmHg or diastolic BP >109 mmHg), hypertensive patients shall be treated in accordance with current guidelines for the management of arterial hypertension
- History of severe systemic disease such as terminal carcinoma, renal failure (or current creatinine >200  $\mu$ mol/l), cirrhosis, severe dementia, or psychosis

Statistical Analysis Plan  
Test product: Revacept  
EudraCT number: 2011-001006-10  
Date 10.06.2019

- Current severe liver dysfunction (transaminase level greater than 5-fold over upper normal range limit)
- Active autoimmune disorder such as systemic lupus erythematosus, rheumatoid arthritis, vasculitis or glomerulonephritis
- Known atrial fibrillation or other clinically significant ECG abnormalities (at present)
- Acoustic window that does not allow for TCD recording
- Subjects who are compulsorily detained for treatment of either a psychiatric or physical illness (e.g. infectious disease)
- Ongoing drug or alcohol abuse

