**Table 6-1: Definitions of protocol deviations**

No.	Criterion	Major deviation (violation)
1	Any of the inclusion criteria answered with 'No' Answers will be checked by other sources in the CRF - if possible	Yes or otherwise declared in the definitions in blind review report
2	Any of the exclusion criteria answered with 'Yes' Answers will be checked by other sources in the CRF - if possible	Yes or otherwise declared in the definitions in the blind review report
3	Patient did not receive the study medication as planned	Yes

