### 7.3 Handling of Drop-outs or Missing Values

Missing values for the primary analyses at Visit 3 respectively 5 will be imputed by the last observation carried forward approach. This means patients who dropped out before Visit 3 respectively 5 will be counted as non-responder.

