## 8.4 Efficacy analysis

All statistical tests will be performed two-sided and will be interpreted in a descriptive-exploratory way. Test for numerical data will be performed under normality assumptions using ANOVA. In addition normality of distribution will be checked based on goodness of fit tests. If normality can not be assumed sensitivity analyses will be performed using the Wilcoxon test. Two-sided confidence intervals (CIs) will be displayed for important variables. Appropriate methods will be used to derive confidence intervals, depending on data nature and distribution.

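### SAP 8.4.3 prints an NIHSS maximum of 62, reached only if an undefined option 9 counts as nine points on each limb item (42 on graded ratings), and the Visit 5 and 6 comparisons leave out the Visit 2 total.

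*SAP*

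**What the plan says.** SAP 4.1 lists neurological status by NIH Stroke Scale among the efficacy endpoints. SAP 8.4.3 places the scale at Visits 2, 5 and 6 and prints its 15 items, "with rating options on the scale 0, 1, 2, 3, 4 and 9 depending on the single item". In the printed table, 9 is offered only for the four limb motor items (5a, 5b, 6a, 6b), next to 0 to 4. The last row gives a maximum total of 62.

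Two analyses follow. Item ratings are tabulated by visit and compared with a Mantel-Haenszel chi-square test. For the total: "The total score of the NIH Stroke Scale will be compared between groups by visit using ANOVA". Under SAP 8.4 there is a fallback: "If normality can not be assumed sensitivity analyses will be performed using the Wilcoxon test". No covariate or change from Visit 2 is planned for this endpoint.

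On missing data, protocol 9.3.3 defers to the SAP: "Rules on how missing values of efficacy variables will be replaced are to be described in the Statistical Analysis Plan". SAP 7.3 answers with one rule: "Missing values for the primary analyses at Visit 3 respectively 5 will be imputed by the last observation carried forward approach".

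**The concern.** A jump from 4 to 9 on the limb items alone looks like a code and not a grade, yet the printed maximum works only if 9 is a number of points. A programmer deriving the total has that maximum as the only instruction, and it points towards adding 9. If 9 does mean that the limb could not be scored, patients with an unassessable limb would get totals higher than the worst graded deficit could produce. In the item-wise tests, 9 would stand as the most severe category. For scale, protocol Appendix B calls a stroke major from 4 NIHSS points.

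The second issue is separate and smaller. A Visit 2 total is collected for the same patients, but the Visit 5 and Visit 6 comparisons ignore it, so between-patient differences present at treatment remain in the error term.

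**Working it through.** **1. Reproducing the printed maximum** (item table, SAP 8.4.3)

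- Top ratings of the 11 non-limb items (1a, 1b, 1c, 2, 3, 4, 7, 8, 9, 10, 11): 3 + 2 + 2 + 2 + 3 + 3 + 2 + 2 + 3 + 2 + 2 = 26.
- Four limb items with 9 counted as points: 26 + 4 × 9 = 62. This is the SAP's figure.
- Four limb items on the graded ratings: 26 + 4 × 4 = 42.
- With 0, 1, 2, 3 or 4 limbs at 9 and the others at 4, the total is 42, 47, 52, 57 or 62. Only four 9s, all counted as points, give 62.

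**2. Looking for a rule elsewhere**

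- Protocol 7.2.4 refers to Appendix A for the neurological scores. Appendix A prints the modified Rankin Scale and the Barthel Index, not the NIHSS.
- Protocol 10.11.1 tells sites to write NA, NK or ND for unavailable CRF data. 9 is not among these.
- SAP 7.3 covers the primary analyses at Visits 3 and 5. It has nothing on a single unscored item, and nothing for Visit 6.

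So 9 is undefined, and no rule says how a total containing it is formed.

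**3. Size of one 9 counted as points** (50 patients per arm, SAP 3.3)

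- Compared with scoring the limb 0: 9/50 = 0.18 points on the arm mean.
- Compared with a graded 4: (9 − 4)/50 = 0.10 points.

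The documents give no standard deviation. As an illustration, take SD 2 or 5 as assumptions, one such record in one of two arms compared, and the added 9 unrelated to the rest of the score:

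- Variance ratio in the affected arm: 1 + 81 × 0.02 × 0.98/SD² = 1.397 (SD 2) or 1.064 (SD 5).
- Standard error of the difference: √[(SD² × ratio + SD²)/50] = 0.438 or 1.016.
- Shift: 0.18/0.438 = 0.41 or 0.18/1.016 = 0.18 standard errors. A larger SD makes it smaller.
- If 9s are spread evenly over the arms, the expected shift is zero and only noise is added. One record in each arm multiplies the standard error by √ratio = 1.18 or 1.03.

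**4. Leaving out the Visit 2 total**

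The variance left after linear adjustment is 1 − ρ², where ρ is the within-arm correlation of the Visit 2 total with the later total. ρ is not in the documents. At assumed values of 0.3, 0.5 and 0.7 the remaining variance is 0.91, 0.75 and 0.51 of the unadjusted variance.

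**The case against.** - **The table agrees with itself.** This is true: 62 follows from the printed options. A reader might infer that 62 is simply wrong and that 9 is a not-assessable code. The documents do not say so. What they support is an undefined option and a missing scoring rule.
- **No 9 may ever have been recorded.** This stands. If none was, only the printed maximum is affected.
- **Existing steps will catch it.** The item frequency tables would show any 9s. The Wilcoxon analysis limits their leverage, but it is conditional on non-normality and still ranks the inflated totals. The blinded data review (SAP 7.2) is a suitable occasion to settle the rule. None of these supplies it.
- **The study is exploratory.** SAP 7.5 has no confirmatory hypotheses, so error control is not at stake. A descriptive endpoint still needs a defined score.
- **Unadjusted ANOVA is valid.** It is unbiased under randomisation, and the by-visit comparison will display any Visit 2 imbalance. A reader might infer bias in the later comparisons; the documents do not support that. The loss is precision only, and displaying Visit 2 does not recover it.
- **Per-protocol set.** "NIHSS score > 18" is an exclusion criterion, and for exclusion criteria Table 6-1 says "Answers will be checked by other sources in the CRF - if possible". A reader might infer that patients would be wrongly excluded because a 9 inflated their total. Neither document says that the Visit 2 total is used for this check, and deviations are classified by people at a blinded meeting. This is only a place where the same scoring rule should apply if Visit 2 totals are used.

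**Conclusion.** The point holds as a scoring gap with a lesser analysis issue attached. The printed 62 requires 9 to be summed on all four limb items; the graded maximum is 42. Nothing in either document defines 9 or excludes it from the total-score ANOVA or the item-wise tests. Following the printed maximum would add 9 points per such limb, or 0.18 points to a 50-patient arm mean per record (0.10 compared with a graded 4). Whether this affects any result depends on how often 9 was recorded and in which arms, which the documents do not show. The standard-error figures rest on assumed SDs. No upper limit for the SD at Visits 5 and 6 can be taken from the entry limit of 18, because later totals can exceed it.

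The omitted Visit 2 adjustment costs precision, not validity, and its size depends entirely on the assumed correlation. Both matters concern the correctness and precision of a descriptive endpoint and are worth settling before unblinding.

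**What to change.** In SAP 8.4.3, before unblinding:

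1. Define 9. If it is a severity grade, say so and keep 62.
2. If it is a non-numeric code, exclude it from the sum and from the ordered item tests, show it as a separate row in the frequency tables, and print the maximum as 42.
3. State how the total is formed when a limb is coded 9, identically at Visits 2, 5 and 6. One option is the sum of the scored items, with a sensitivity analysis that sets the total to missing. Use the same rule if Visit 2 totals serve in the per-protocol check.
4. Compare Visit 5 and Visit 6 totals by ANCOVA with the Visit 2 total as covariate (rank ANCOVA if normality fails). Keep all patients in the analysis and state in advance how a missing Visit 2 total is handled.
5. Add a sensitivity analysis for any Visit 2 score known to have been taken after the start of the infusion. Protocol 7.1.2 lists the neurological assessment ahead of the infusion, but states pre-dose timing only for the platelet tests, the antibody sample and the first pharmacokinetic sample.

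The cost is SAP wording, one derivation rule, one model term and a look at Visit 2 timing where it is recorded. No new assessments are needed.

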### 7.6 General Calculation Rules

Binary, categorical and ordinal parameters will be summarised by means of absolute and percentage numbers (including 'missing data' as valid category at visit 1). Numerical data will be

summarised by means of standard statistics (i.e. number of available data, mean, standard deviation, minimum, median, maximum, lower and upper quartile). Wherever useful, the summary statistics will be presented by stratification according to centers and/or visit. In addition, adequate figures (e.g. bar charts, Box-Whisker-Plots) will be presented to summarise the results for some parameters.

All statistical tests will be performed two-sided and will be interpreted in a descriptive-exploratory way. Two-sided confidence intervals (CIs) will be displayed for important variables. Appropriate methods will be used to derive confidence intervals, depending on data nature and distribution. All safety and tolerability data will be presented in a purely descriptive manner as outlined below.

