#### **8.4.4 Cerebral lesion analysis by DWI-NMR 1 day after CEA and correlation to neurological status**

Cerebral lesions: Number of cerebral lesions in perfusion area of carotid artery stenosis assessed at Visit 5 by the central reading lab ([name], Tübingen).

- back
- front right
- front left
- and total

Groups will be compared for

- change of number of DWI lesions V5 compared to V1 (delta number of lesions)
- percent change of number of DWI lesions V5 compared to V1

using ANOVA.

In addition groups will be compared for

- rate of incidence of patients with DWI lesions after treatment (V5)
- rate of incidence of patients with new DWI lesions after treatment (V5)
- rate of patients with DWI lesions in V5 reduced compared to V1

using Fisher's exact test.

Neurological status: Modified Rankin Scale (MRS) assessed at Visit 6:

0	No symptoms at all
1	No significant disability despite symptoms; able to carry out all usual duties and activities
2	Slight disability; unable to carry out all previous activities, but able to look after own affairs without assistance
3	Moderate disability; requiring some help, but able to walk without assistance
4	Moderately severe disability; unable to walk without assistance and unable to attend to own bodily needs without assistance
5	Severe disability; bedridden, incontinent and requiring constant nursing care and attention
6	Dead

The following correlations will be performed by treatment group:

- Cerebral lesions of back area of carotid artery stenosis x MRS
- Cerebral lesions of front right area of carotid artery stenosis x MRS

Statistical Analysis Plan  
Test product: Revacept  
EudraCT number: 2011-001006-10  
Date 10.06.2019

- Cerebral lesions of front left area of carotid artery stenosis x MRS

Correlation analysis will be performed by calculating the Pearson correlation coefficient. In a subgroup analysis, only patients will be compared who did not receive any change in the concomitant medication with anti-platelet activity (=rescue medication) between the initial assessment at V1 and the follow-up investigation at V3 / V5.

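### The NIHSS comparison has no rule for death and no adjustment for the Visit 2 score, and the Rankin scale, which does score death, is never compared between arms

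*SAP*

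**What the plan says.** **NIHSS.** SAP 8.4.3 gives the timing: "The neurological status was assessed at Visit 2, Visit 5, and Visit 6 by the NIH stroke scale". It gives the analysis as: "The total score of the NIH Stroke Scale will be compared between groups by visit using ANOVA". No covariate is named. The item table has no value for death, and nothing in the section assigns one.

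**Missing values.** Protocol 9.3.3 defers to the SAP: "Rules on how missing values of efficacy variables will be replaced are to be described in the Statistical Analysis Plan". SAP 7.3 answers with one rule: "Missing values for the primary analyses at Visit 3 respectively 5 will be imputed by the last observation carried forward approach". It then explains: "This means patients who dropped out before Visit 3 respectively 5 will be counted as non-responder". Visit 6 has no rule. SAP 7.6 shows missing data as a category only at Visit 1 ("including 'missing data' as valid category at visit 1").

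**Rankin.** The scale includes 6 for death (Protocol Appendix A, SAP 8.4.4) and is collected at Visits 2 and 6 (Protocol 7.1, 7.1.2 and 7.1.6). SAP 8.4.4 introduces it as "Neurological status: Modified Rankin Scale (MRS) assessed at Visit 6" and uses it only for Pearson correlations with lesion counts within each treatment group. Neither document compares it between arms.

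**Deaths.** SAP 8.4.5 compares all-cause and stroke-related death between groups by Fisher's exact test, cumulatively from before treatment to 12 months. SAP 8.1 tabulates discontinuation due to death by treatment group.

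**The concern.** Neurological status is a listed efficacy endpoint in both documents. In symptomatic carotid stenosis death can be the end point of neurological deterioration, and the plan itself lists stroke-related death. A by-visit comparison of NIHSS totals that leaves out patients who died is conditioned on survival, and survival is itself an outcome after randomisation. If the patients who die would have scored worse than average, removing them lowers their arm's mean, and a lower mean reads as better status. Carrying the Visit 2 score forward avoids the removal but records a death as an unchanged patient.

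The trial collects a scale that includes death at the same 3-month visit and does not use it for this purpose. The protocol synopsis foresees combining these data with later studies, so a survivors-only estimate could be reused without its condition attached.

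**Working it through.** **1. Check of the scored variable.** The printed NIHSS maximum is 62. Adding the highest option of the 15 items gives 3+2+2+2+3+3+9+9+9+9+2+2+3+2+2 = 62, which reproduces it. Without the four 9 codes the sum is 42. Neither total has a place for death.

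**2. Tracing a death through the rules.**

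| Death occurs | Rule that applies | Entry in the NIHSS ANOVA |
|---|---|---|
| Before Visit 5, SAP 7.3 not read to cover NIHSS | none | missing at Visits 5 and 6 |
| Before Visit 5, SAP 7.3 read to cover NIHSS | carry forward at Visit 5 only | Visit 2 score at Visit 5; missing at Visit 6 |
| Between Visits 5 and 6 | none | missing at Visit 6 |

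The Visit 2 score appears to be pre-dose, but this is inferred from the order of procedures in Protocol 7.1.2. The non-responder sentence in SAP 7.3 has a meaning for a yes/no outcome and none for an NIHSS total. Visit 5 falls at the latest about 10 days after treatment (3 + 5 days to Visit 4, plus 24 + 24 hours, Protocol 7.1). Visit 6 is at 3 months and has the longer exposure to deaths.

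**3. Shift from leaving deaths out.** With n patients and d deaths:

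survivors' mean − full-arm mean = −[d/(n − d)] × (mean of those who die − full-arm mean)

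With n = 50 (SAP 3.3) the multiplier is 2/48 = 0.042 for 2 deaths, 4/46 = 0.087 for 4 and 6/44 = 0.136 for 6. The shift is zero if those who die are typical of the arm, and it reverses if they score below the arm mean.

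**4. Illustration.** The documents give no NIHSS distribution and no death rate, so these inputs are assumptions:
- 50 per arm and the same NIHSS distribution in both arms: negative binomial, size 1.2, mean 4 before a cap at 18. The cap is the eligibility limit in Protocol 5.2.2.
- Follow-up score = baseline −1, 0 or +1, not below 0.
- Deaths in one arm only; 4,000 runs.
- Four deaths correspond to 8% of 50. Protocol 1.3 uses 8% for serious adverse events including deaths; using it as a death count is an assumption.
- In the middle case the chance of dying is proportional to the score plus 1.

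Mean difference, arm with deaths minus other arm (negative = arm with deaths looks better). The percentage is the share of runs in which that arm has the better mean.

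| Deaths | Who dies | Left missing | Visit 2 score carried forward |
|---|---|---|---|
| 2 v 0 | random | 0.02 (49%) | 0.02 |
| 2 v 0 | sicker likelier | −0.11 (55%) | 0.01 |
| 2 v 0 | the worst two | −0.46 (74%) | 0.00 |
| 4 v 0 | random | 0.00 (50%) | −0.01 |
| 4 v 0 | sicker likelier | −0.25 (62%) | 0.01 |
| 4 v 0 | the worst four | −0.81 (86%) | 0.01 |
| 6 v 0 | random | −0.03 (52%) | −0.03 |
| 6 v 0 | sicker likelier | −0.40 (69%) | −0.02 |
| 6 v 0 | the worst six | −1.11 (93%) | −0.01 |

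By the formula in step 3, −0.25 and −0.81 with 4 deaths mean that those who die sit about 0.25 × 46/4 = 2.9 and 0.81 × 46/4 = 9.3 points above the arm mean. The carry-forward column is near zero because the simulated scores hardly change on average.

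**5. What the separate death test would show.** For d/50 v 0/50 the two-sided Fisher p-value is 2 × C(50,d)/C(100,d):
- d = 2: 2 × 1,225/4,950 = 0.49
- d = 4: 2 × 230,300/3,921,225 = 0.12
- d = 6: 2 × 15,890,700/1,192,052,400 = 0.027

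**The case against.** **Deaths are compared elsewhere.** SAP 8.4.5 covers the time points at which NIHSS is analysed, and SAP 8.1 tabulates deaths as a reason for discontinuation. A reader might infer that an excess of deaths could go unseen; the documents do not support that. What remains is that the death table does not change what the NIHSS comparison measures, and 2 or 4 deaths against none would not stand out by p-value.

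**The plan does not reward death as such.** A reader might infer that it always favours the arm with more deaths. Step 4 shows otherwise: the difference is about zero when deaths are random or carried forward. The advantage needs deaths left missing and concentrated in sicker patients. The carry-forward case is itself uncertain, because SAP 7.3 speaks of primary analyses and SAP 8.4.1 applies the rule to microembolic signals.

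**Scoring death at 42.** A reader might measure the problem by giving each death the scale's top score. In the example with 4 deaths that moves the difference to between +2.3 and +3.0. This reflects the assumed score, which the SAP does not assign, and not the bias of the planned analysis.

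**Rankin is not a listed endpoint for between-arm comparison.** True: both documents name NIHSS, and reporting deficit in survivors beside mortality is a recognisable choice. But the SAP does not state that choice.

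**A rank test is already planned.** SAP 8.4 adds a Wilcoxon test if normality fails. It would still leave out patients without a score.

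**The study is exploratory.** This holds and limits the consequence to a misleading description.

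**Conclusion.** The gap in the rules is established from the text: no handling of death in the NIHSS comparison, no missing-data rule at Visit 6, no adjustment for the Visit 2 score, and no between-arm use of Rankin. The NIHSS result at Visit 6 describes survivors who were assessed, and nothing in the plan says so.

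The size cannot be fixed from the documents. Under the stated assumptions, with 4 versus 0 deaths, it runs from about 0 (random deaths, or scores carried forward) to 0.25 to 0.81 points in favour of the arm with deaths (sicker patients die and are left missing). It grows with the number of deaths and with how far above the arm mean those patients scored. Deaths remain visible in SAP 8.4.5. In an exploratory study this is a cheap improvement to a secondary comparison, not a threat to a confirmatory claim.

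**What to change.** Specify in the final SAP, before the blind is broken:

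1. Compare Rankin at Visit 6 between arms with death = 6, using an ordinal model or rank test adjusted for the Visit 2 Rankin score.
2. Adjust the NIHSS comparisons at Visits 5 and 6 for the Visit 2 NIHSS score.
3. Show the number of deaths per arm beside each NIHSS summary, and state that the comparison is among patients alive and assessed.
4. State whether the carry-forward rule in SAP 7.3 applies to NIHSS.
5. Give an NIHSS analysis with deaths at the worst rank as a sensitivity analysis only. As a composite that treats every death as neurological failure, it is debatable as the main result.

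No new data are needed, because Rankin and NIHSS are already collected at Visit 2. The cost is about one extra exploratory table. The drawback is that Rankin with death = 6 also counts non-neurological deaths, so it should be read beside the all-cause and stroke-related death counts in SAP 8.4.5.
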